Studies have revealed the benefits of acupuncture for numerous disorders including, but not limited to, sleep disorders, anxiety, cardiovascular disease, and epilepsy.¹ While previous research seems to support the use of acupuncture as a possible treatment for anxiety and related disorders^{1,6} little research has focused on anxiety, irritability, and agitation (AIA) symptoms in patients with Alzheimer's Disease and Alzheimer's Disease Related Dementias (AD/ADRD). This is not to say that this population has not been a source of interest in previous acupuncture literature, as research has already demonstrated that it is a tolerable and safe procedure for this patient subset.² However, most studies have focused on its effect on cognitive symptoms, as opposed to neuropsychiatric symptoms.

Anxiety, irritability, and agitation symptoms are extremely prevalent, occurring in 40-100% of AD patients.³ These symptoms lead to increased morbidity and mortality, accelerated nursing home placement, decreased quality of life and increased health costs for the patient. They also cause additional stress and cost for the caregiver and family members.⁴ Pharmaceutical options are sparse, and the few that ameliorate even a small subset of these symptoms also significantly increase the risk of cerebrovascular events and death.⁵ The prevalence of these symptoms, their subsequent effects, and the scant treatment options are forcing researchers to consider more holistic alternatives, such as acupuncture.

The autonomic nervous system (ANS) plays a primary role in AIA symptoms. It is responsible for our “fight or flight” emergency response and our eventual relaxation. Therefore, when the ANS does not perform correctly, AIA symptoms can result. When the ANS initiates the sympathetic nervous system, heart rate increases as it prepares the body for action. Conversely, when the parasympathetic system engages, heart rate slows and calms the body down. Much of this is controlled by the vagal nerve. As a result, heart rate variability (HRV) becomes a reliable measure of autonomic function or dysfunction.¹¹ More specifically, when the ANS is functioning properly, the vagal nerve has more control over heart rate and this leads to greater variability, as the nerve is constantly reacting to and adapting to external stimuli. If the ANS is dysfunctional, the vagal nerve will not have as much control and, instead, the heart will beat in a steadier, more metronome-like fashion. Skin conductance (SC) will also be utilized in this sub-study. Skin conductance measures the activation of sweat glands. Sweat is an arousal response controlled by the ANS and is therefore another reliable measure of ANS function or dysfunction.⁸

It is suggested that acupuncture aids in restoring balance between sympathetic and parasympathetic activity.¹ Specifically, it has been shown to affect the hypothalamus, medulla oblongata, dorsomedial prefrontal cortex, and the ventrolateral periaqueductal gray, among others¹. These brain areas encompass a large portion of the regions involved in autonomic regulation. Previous research has revealed that acupuncture influences autonomic activity as measured by HRV and SC.^{7,9} This study aims to understand the effects of acupuncture on AIA symptoms in AD/ADRD as they are presented in outward behavior, HRV and motor restlessness as measured by the BioStamp nPoint, and SC. The location of needle points were selected based on commonly used points in other research studies involving anxiety, agitation, and irritability in persons with and without dementia.¹⁰

II. SPECIFIC AIMS

The purpose of this study is to discover whether acupuncture has an influence on HRV, SC, motor restlessness, and self-reported or rated behavioral expression of symptoms in individuals with AD/ADRD. This will identify any possible potential for a new, nonpharmacological therapy for treating AIA symptoms in this complicated population.

We hypothesize the following:

- 1.) Acupuncture will acutely benefit autonomic dysregulation in AD/ADRD subjects with AIA as indexed by reduced HRV and SC during treatment compared to pre-treatment rest.
- 2.) There will be a short-term benefit of acupuncture treatment on autonomic regulation as indicated by increased mean HRV and less motor restlessness on actigraphy and on behavioral symptoms as indicated by lower reported score on the Profile of Mood States (POMS)-abbreviated and fewer AIA symptoms documented by the subject or study partner during the observation period following the treatment compared to the pre-treatment observational day.
- 3.) Individuals without AIA, both CU and AD/ADRD, will reap similar benefits on autonomic regulation and behavioral symptoms as those with AIA.

III. SUBJECT SELECTION

Inclusion: Study subjects should meet all the inclusion criteria during screening evaluations to be entered into the study.

- Ages 55-95 inclusive, male or female.
- Diagnosis of CU, or probable AD, FTD or DLB as determined by established clinical criteria at screening¹⁴.
- For the AIA symptomatic groups, a score of > 2 for Severity on at least 1 of the AIA-relevant items on the NPI-Q, i.e., Anxiety, Irritability/Lability, Agitation or Aggression.
- For the CU and no neuropsychiatric symptoms group, NPI-Q score must be 0 for AIA-relevant items, i.e., Anxiety, Irritability/Lability, Agitation or Aggression.
- No concurrent use of therapies with prohibitive effects on interpretation of HRV and SC measurements, e.g., those with major direct adrenergic or anticholinergic activities.
- Stable doses (>2 weeks) of concurrent dementia or psychiatric drugs for those applicable.

Exclusion: Study subjects should not meet any exclusion criteria during screening evaluations or they will be excluded from entry into the study.

- Atrial or junctional arrhythmias or other cardiac conditions, including pacemakers or other implantable devices that affect RR intervals or their measurement.
- AIA symptoms or dementia so severe that subject cannot assent and cooperate with all study procedures or requires immediate rescue medication for behavioral control.
- Seizure disorders or other potentially confounding medical, neurological or longstanding psychiatric illnesses.

Subjects will be recruited from the parent AIA study. The parent study, “A Test-Retest Reliability Study of Non-Invasive Measures of Autonomic Nervous System Physiology and

Actigraphy as Biomarkers of Agitation, Irritability and Anxiety in Alzheimer's Disease and Alzheimer's Disease Related Dementias" (protocol: 2018P000817), is an ongoing study that is investigating autonomic dysfunction as it relates to AIA in individuals with and without dementia. The parent AIA study will be recruiting from The Massachusetts Alzheimer's Disease Research Center Longitudinal Cohort (MADRC-LC), which undergoes annual in-person assessments with standardized clinical and neuropsychological rating instruments and all have expressed an interest in participating in additional research. The parent study will also be recruiting from other MGH neurology subspecialty clinics along with the Principal Investigator's (treating physician) clinic. Finally, individuals may be recruited for the parent study through internet trial postings through MGH and Brigham and Women's Hospital, along with fliers at approved MGH locations.

Eligible subjects scheduled for in-person visits in the parent study will be informed of the sub-study option during the consenting process on day one of parent study activities. They will be informed that this is completely voluntary and independent of their participation and eligibility in the parent study.

IV. SUBJECT ENROLLMENT

Subjects will be informed of the acupuncture sub-study during the consenting process on day one of the parent AIA study. Should a subject not want to partake in the sub-study, their participation in the parent study will not be affected. Subjects who are interested will be given ample time to review the study procedures and ask any questions they may have. If they wish to speak with the licensed acupuncturist who would be performing the procedure, they will be given that opportunity. [name], [name], [name], or [name], the licensed managing acupuncturist will obtain written informed consent from each participant, at the start of the screening visit. The consenting discussion of the sub-study will include all of the required elements of informed consent, including the purpose of the research, the procedures to be followed, the risks and discomforts, as well as potential benefits associated with participation. This discussion will also make very clear that this is a completely optional sub-study and will not affect participation in the parent AIA study.

Should a subject agree to participate in the acupuncture sub-study, sign consent, but subsequently change their mind, they will not be punished. Signing consent for the sub-study will not bind the participant into receiving acupuncture treatment. Repealing consent will not affect participation in the parent study in any way. Similarly, should a subject wish to terminate the acupuncture treatment mid-session, the licensed acupuncturist will immediately remove the needles and ensure the subject is safe to return home.

This study will be conducted in compliance with Title 21 Part 50 of the United States of America Code of Federal Regulations (CFR), Federal Regulations, and ICH Guidance Documents pertaining to informed consent.

V. STUDY PROCEDURES

The sub-study will be introduced to subjects during the consenting process for the AIA parent study. It will be emphasized that participation in the acupuncture portion as a sub-study is strictly voluntary and will in no way affect participation or eligibility in the parent study.

After the second day of participation in the parent study, individuals who would like to participate in the sub-study will receive a 20-minute acupuncture session. Before beginning, participants will be asked to complete the POMS-abbreviated mood questionnaire. We will employ a modified standardized acupuncture protocol with points used in previous research studies¹⁰ to effectively reduce symptoms of anxiety and depression in individuals with dementia. The treatment will include commonly used acupuncture points for a total of 9 needles located on the top of the head, forehead, hand, wrist, lower leg, ankle and top of foot at approximately 0.5 – 1 cm depth. Needles will be placed at acupoints GV20 (x1), Yintang (x1) and left HT-7 (x1), left LI-4 (x1), right PC-6 (x1), bilateral ST- 36 (x2), right KD- 3 (x1) and left LV-3 (x1). A licensed acupuncturist credentialed by MGH will perform all acupuncture treatments. Upon insertion, the study acupuncturist will manipulate the needles to elicit the “de qi” sensation common in acupuncture treatments. Participants will then repeat the POMS-abbreviated shortly following the removal of acupuncture needles. Finally, participants will repeat the POMS a third time before removing the BioStamp nPoint the following day, roughly 20 ±4 hours after treatment.

The data collected for this sub-study will consist of observed behavioral expression and reported AIA symptoms and mood, HRV, SC, and motor restlessness and actigraphy as measured by the BioStamp nPoint. Upon completing the parent study’s activities, subjects will remain connected to the SC measuring device, which will record SC throughout the acupuncture session. Additionally, subjects will wear the BioStamps home after completing the treatment. These will provide roughly 22 hours of HRV and actigraphy recordings post-acupuncture session. Finally, CU subjects or AD/ADRD study partners will be asked to complete a behavior diary. This will provide us with an understanding of the subjects’ behavior and symptoms for a day following acupuncture treatment. This diary will be returned via mail with the BioStamps and third POMS. Once these are received, data will be entered into the EDC and the participant will have completed the study.

VI. BIOSTATISTICAL ANALYSIS

General Considerations: Statistical analyses will begin with scatterplot inspection, and descriptive statistics. All variables will be checked for normality and other parametric assumptions, with appropriate transformation applied if necessary for parametric analyses. If normality assumptions cannot be met, non-parametric test equivalents will be used. Missing data, if any, will be characterized, with scrutiny towards identification of any patterns of missingness. Demographic and clinical characteristics of the sample will be evaluated and potentially important differences in these characteristics (e.g., age, sex, education, non-psychiatric medication class) by diagnoses will be assessed using χ^2 tests or Student t-tests (and/or ANOVA) for categorical and quantitative variables, respectively. Demographic or clinical variables that differ between groups will be included as covariates. $P < 0.05$ will be considered significant. This study is a pilot study, largely descriptive and exploratory. Multiple comparison corrections will not be applied in the primary analyses.

We hypothesize that the acupuncture will acutely benefit autonomic dysregulation in AD/ADRD subjects with AIA as indexed by reduced HRV and SC during treatment compared to pre-treatment rest. Therefore, we will explore any differences in HRV/SC after during/after treatment compared to pre-treatment rest.

In HRV analysis, more than 70 variables can be calculated in time- and frequency-domains,¹² including those mentioned previously: mean RR interval, SDNN, RMSSD, NN50 counts and three spectral frequency bands (very low, low and high) as well as total spectral power. In the time domain, SDNN reflects all the cyclic components responsible for variability in the recording epoch, so represents total variability. RMSSD is thought to reflect vagal tone and is relatively free of respiratory influences. In the frequency domain, low frequency (LF) band is thought to reflect a mix of sympathetic and vagal activity, while the high frequency (HF) band reflects vagal tone. The ratio LF/HF is often used as an index of overall sympathovagal balance. In SC analyses, resting tonic SC levels, non-specific skin conductance response (NS-SCR) amplitudes and frequencies occurring during tonic recording, and event-related skin conductance response (“ER-SCR”, as with acoustic startle or an emotional stimulus) are the common measures. NS-SCR frequency is often interpreted as reflecting background sympathetic arousal and startle ER-SCR as the event-related sympathetic arousal responsiveness. Our analysis will explore any differences in post-treatment HRV/SC compared to pre-treatment.

We also hypothesize that there will be a short-term benefit of acupuncture treatment on autonomic regulation and behavioral symptoms as indicated by increased mean HRV, less motor restlessness on actigraphy, lower reported score on the POMS-abbreviated, and fewer observational AIA symptoms documented by subject or study partner during the observation period following the treatment compared to the pre-treatment observational day. Therefore, any changes in these measurements will be explored.

VII. RISKS AND DISCOMFORTS

The risks associated with acupuncture are like any procedure that involves the insertion of needles through the skin. These include but are not limited to fainting, bleeding, infection, increased pain, nerve and tissue damage, needle breakage. None of these risks are common. The acupuncturists are fully trained and licensed and will take every precautionary measure to avoid any adverse effects.

VIII. POTENTIAL BENEFITS

It is possible that some of the patients will derive direct benefit from participation in the acupuncture. If any patient wishes to continue acupuncture, the licensed managing acupuncturist will provide them with a list of competent and validated practitioners in their community.

Moreover, it is anticipated that findings from these studies will help advance brain research generally, and in understanding the possible benefits of acupuncture on AIA symptoms in AD/ADRD.

IX. MONITORING AND QUALITY ASSURANCE

The PI, [name], will ultimately be responsible for the validity and integrity of the data collected at the MGH site, and for ensuring that the study is conducted in accordance with the IRB-approved protocol. After data is collected and recorded on forms, the study coordinator may input the data into the Partners approved REDCap. Entries will be reviewed for accuracy and completeness by a second study coordinator. Finally, the PI or her designee (Co-I) will conduct monthly reviews to check that data in REDCap accurately reflects the data collected on the original data capture forms. The research team (PI, Co-I, research coordinators) will subsequently meet to discuss the results of this review, as well as case report forms and source documentation.

All electronic documentation will be stored on password-protected devices in locked cabinets located in secured areas. Paper forms will be stored in locked cabinets located in secured areas. [name] will ultimately be responsible for the accuracy of the data.

Subjects will be monitored for adverse events from the time they sign consent until completion of their participation in the study. For the purposes of this study, an adverse event (AE) will be defined as any unfavorable or unintended sign (including a clinically significant abnormal laboratory finding, for example), symptom, or disease temporally associated with the study. Stable chronic conditions (e.g. arthritis) that are present prior to the start of the study and do not worsen during the trial will NOT be considered adverse events. Chronic conditions that occur more frequently (for intermittent conditions) or with greater severity are considered as worsened and therefore would be recorded as adverse events.

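### Hypothesis 1 counts a fall in HRV as benefit, against the protocol's own rationale and Hypothesis 2, and the reversed sign is not explained

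*Combined protocol and SAP*

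**What the plan says.** Section II, Hypothesis 1, predicts an acute benefit in AD/ADRD subjects with AIA, "as indexed by reduced HRV and SC during treatment compared to pre-treatment rest". Section VI repeats the prediction almost unchanged: "acupuncture will acutely benefit autonomic dysregulation in AD/ADRD subjects with AIA as indexed by reduced HRV and SC during treatment".

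The background text before section II explains how each measure is to be read. For HRV, "when the ANS is functioning properly, the vagal nerve has more control over heart rate and this leads to greater variability"; when the system is dysfunctional, "the heart will beat in a steadier, more metronome-like fashion". For SC, "Sweat is an arousal response controlled by the ANS".

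Hypothesis 2 in section II gives the direction for the period after treatment: "There will be a short-term benefit of acupuncture treatment on autonomic regulation as indicated by increased mean HRV". Section VI restates it, listing "increased mean HRV, less motor restlessness on actigraphy, lower reported score on the POMS-abbreviated".

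The analysis attached to Hypothesis 1 in section VI carries no direction: "we will explore any differences in HRV/SC after during/after treatment compared to pre-treatment rest". The same section describes the study as a pilot that is mainly descriptive and exploratory.

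**The concern.** In Hypothesis 1 a single adjective governs two measures that, on the protocol's own account, should move in opposite directions when autonomic regulation improves. Lower SC means less arousal. Lower HRV, in the background text, means weaker vagal control.

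Because the analysis only looks for differences, the hypothesis is the only place that tells a reader which HRV change during the session supports benefit. Taken literally, a fall would be reported as the hypothesised benefit and a rise as evidence against it. Hypothesis 3, which expects similar benefits in people without AIA, inherits the same ambiguity.

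**Working it through.** No arithmetic applies: the documents give no sample size, effect size or power figure that bears on the direction. The check is to set the statements side by side.

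| Place | Period and comparator | HRV change counted as better | SC change counted as better |
|---|---|---|---|
| Background, before section II | General account of autonomic function | Up | Down (arousal measure) |
| Section II, Hypothesis 1 | During treatment vs pre-treatment rest | **Down** | Down |
| Section VI, Hypothesis 1 repeated | Same | **Down** | Down |
| Section II, Hypothesis 2 | Observation period after treatment vs pre-treatment observational day | Up | Not stated |
| Section VI, Hypothesis 2 restated | Same | Up | Not stated |

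1. **SC is consistent.** Section VI links the frequency of non-specific SC responses to background sympathetic arousal, so a reduction fits a calming effect. Only the HRV half of Hypothesis 1 conflicts: 1 of its 2 outcomes.

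2. **Could reduced HRV describe the disorder rather than the benefit?** No. The phrase is attached to a comparison of treatment with pre-treatment rest, so it is the predicted change.

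3. **Could a particular index rescue the wording?** Hypothesis 1 names none. Section VI describes SDNN as total variability and RMSSD and high-frequency power as reflecting vagal tone; under the background rationale a fall in any of these points towards dysfunction. LF power is described as mixed sympathetic and vagal, so no direction follows for LF or LF/HF, and the point does not extend to them.

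4. **Is it an isolated slip?** It stands in 2 places, although the second repeats the first. Section VI adds no justification.

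5. **Effect on the analysis.** The comparison is for any difference, so the estimate and a two-sided p-value are the same whichever sign is written. Only the interpretation changes.

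6. **Overlap with Hypothesis 2.** Section VI widens the comparison from during treatment to during or after it, and later to post-treatment against pre-treatment. If the sign of Hypothesis 1 were carried into that later period, post-session HRV would have two opposite definitions of benefit. The text does not say that it is carried over. The comparators differ, so the two results need not agree numerically; the conflict is in what counts as benefit.

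7. **Limit on reach.** Section V describes in-session recording explicitly for SC only. The HRV it describes is the roughly 22 hours after the session. How much in-session HRV will exist cannot be confirmed from this document.

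**The case against.** The strongest counter-argument is that the two hypotheses cover different situations. Hypothesis 1 concerns a 20-minute session in which needles are manipulated to produce a sensation; Hypothesis 2 concerns the observation period afterwards. The background text describes autonomic function in general and makes no prediction for the minutes of needling. An acute fall followed by a later rise is therefore logically possible. This stands as a possibility, but the protocol never states it, and it calls the acute fall a benefit without giving a reason.

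It is also fair to say that nothing operational depends on the sign: there is no one-sided test, success criterion or stopping step tied to it. That is accepted, and it limits the point to interpretation.

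Two further cautions stand. Hypothesis 2 applies the background rationale, so the two are not separate pieces of evidence for the upward direction. And section VI refers to HRV variables as already mentioned, although the text available does not list them earlier; with the parent protocol also out of view, the absence of an explanation can be asserted only for the text available.

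None of this removes the mismatch, which lies in a stated hypothesis and in the analysis section rather than in background prose alone.

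**Conclusion.** The concern holds. Hypothesis 1 gives HRV a direction of benefit opposite to the protocol's rationale and to Hypothesis 2, in sections II and VI, without explanation in the text available. The change in estimates and two-sided p-values is none. What changes is the conclusion that may be drawn about in-session HRV, and so whether a result is reported for or against Hypothesis 1.

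This rests on two readings: that HRV in Hypothesis 1 means overall variability or vagal indices, and that its direction is meant as the predicted treatment effect. It is worth correcting, though not a fault in the test. How far it matters in practice depends on how much HRV is recorded during the session.

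**What to change.** In sections II and VI, give HRV and SC separate directions in Hypothesis 1: HRV expected to rise and SC to fall during treatment relative to pre-treatment rest. State that the HRV direction applies to overall variability and vagal indices, naming them, and not to LF or LF/HF.

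If an acute fall in HRV really is intended as benefit, give the rationale and reconcile it with the background text and Hypothesis 2 before results are interpreted. In either case, say which period each direction covers, so that the wider during-or-after comparison in section VI does not borrow the wrong sign.

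The cost is a wording change in two places. The non-directional analysis can stay; no new data, tests or procedures are needed.

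### Hypothesis 2 reads a change in mean HRV over a day at home as autonomic benefit, but the plan has no way to separate it from a change in how much the subject moved

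*Combined protocol and SAP*

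**What the plan says.** Section II, hypothesis 2, expects a short-term benefit on the regulation of the autonomic system, shown by "increased mean HRV and less motor restlessness on actigraphy" and assessed "during the observation period following the treatment compared to the pre-treatment observational day". Section VI repeats the indicators ("increased mean HRV, less motor restlessness on actigraphy, lower reported score on the POMS-abbreviated") and says only that changes in them will be explored.

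The background text before Section II gives the source of both signals: "HRV and motor restlessness as measured by the BioStamp nPoint, and SC". Section V describes the setting, in which "subjects will wear the BioStamps home after completing the treatment", and the length: "These will provide roughly 22 hours of HRV and actigraphy recordings post-acupuncture session".

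Three features of Section VI matter here:

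- The covariate rule admits only demographic or clinical characteristics that differ between groups.
- HRV is said to yield more than 70 variables. Several are described, but none is assigned to hypothesis 2.
- There is no rule for still or sleep epochs, for matching on activity, or for movement artefact.

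**The concern.** A mean over most of a day is a weighted average over whatever the subject was doing. If HRV differs between still and moving periods, a change in the mix shifts the mean even when HRV within each state is unchanged. Hypothesis 1 uses a resting baseline. Hypothesis 2 has no such condition.

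Nothing else in the plan absorbs the shift. The comparison is before-after within the subject, with no untreated or sham day. The covariate rule concerns differences between groups, so it cannot bring in activity that varies within a subject over time. The day after two study days and a procedure may differ in activity from the day before for reasons unrelated to acupuncture.

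At stake is how an HRV result is read. A rise could be reported as better autonomic regulation when the subject only moved less. With a different HRV metric, the same mechanism could hide a real improvement.

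**Working it through.** The plan gives no sample size, SD, effect size or HRV value, so there is no figure of its own to reproduce. The only inputs from the documents are the 0.05 level (Section VI; two-sided testing is assumed) and the recording length of roughly 22 hours (Section V). All other inputs below are assumptions.

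**1. Shift in the mean from activity mix alone.** Mean = p × (still value) + (1 − p) × (moving value), where p is the share of time still. Assume RMSSD of 35 ms still and 20 ms moving.

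- p = 0.60: 0.60 × 35 + 0.40 × 20 = 29.0 ms
- p = 0.70: 0.70 × 35 + 0.30 × 20 = 30.5 ms, a shift of 1.5 ms (1.5/29.0 = 5%)
- p = 0.75: 0.75 × 35 + 0.25 × 20 = 31.25 ms, a shift of 2.25 ms

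A 10-point rise in still share over 22 hours is 0.10 × 22 = 2.2 more still hours per subject on average.

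**2. Chance of P<0.05 with no change in either state.** Paired t-test, noncentrality = shift × √n / SD of change, assumed SD 6 ms. The nominal rate is 5%.

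| Shift | n = 15 | n = 20 | n = 30 |
|---|---|---|---|
| 1.5 ms | 15% | 19% | 26% |
| 2.25 ms | 27% | 36% | 51% |

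**3. Sensitivity, still share 60% to 70%, n = 15 to 30.**

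- Still/moving gap of 5 ms, SD 6: shift 0.5 ms, 6% to 7%.
- Gap of 10 ms, SD 9: shift 1.0 ms, 7% to 9%.
- Gap of 15 ms, SD 6, with 80% of moving epochs lost to artefact: the means are (0.6 × 35 + 0.08 × 20)/0.68 = 33.24 and (0.7 × 35 + 0.06 × 20)/0.76 = 33.82. The shift is 0.58 ms, giving 6% to 8%.

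**4. Direction, and whether adjustment works.** A separate simulation (20,000 runs per setting) gave treatment no direct effect on HRV. It set mean activity change at −0.5 SD and n = 20, and varied the correlation r between activity change and HRV change. The nominal rate in each direction is 2.5%.

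| r | Significant HRV increase, unadjusted |
|---|---|
| −0.6 | 24.4% |
| −0.3 | 9.1% |
| 0 | 2.6% |
| +0.3 | 0.6% (a significant decrease in 9.5%) |

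After regressing HRV change on activity change, the rate returned to about 2.5% in each direction in every setting. With no shift in activity, the unadjusted test was also near nominal.

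**The case against.** Several stronger readings are tempting, and the documents do not support them.

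- **That a quieter day will read as better regulation.** This needs a metric that rises with stillness. Section VI fixes none. It describes SDNN as capturing total variability, which could fall when activity-driven swings are fewer. The background says only that under sympathetic activation "heart rate increases as it prepares the body for action". That concerns heart rate, not the effect of movement on HRV, which is general physiology brought in from outside.
- **That one finding would be reported as two, or that a shared sensor is a flaw.** Hypothesis 2 offers HRV and restlessness as joint indicators of one construct and nowhere calls them independent. Recording both on one device is harmless in itself, and it is what makes an activity-matched analysis possible.
- **That artefact loss adds to the problem.** In the example above it shrinks the shift, because the average already leans towards still epochs.
- **That the plan prescribes an unadjusted average.** It does not. It is silent on how mean HRV is formed.

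The best argument against the remedy is that less restlessness is itself a hypothesised effect of treatment. Activity is then an outcome and a possible mediator, and matching on it removes any HRV benefit that acts through calming. This stands. It means the matched analysis should accompany the main comparison, not replace it or decide whether it counts. The study also labels itself an exploratory pilot, which limits the weight of the point. Activity matching does not repair the uncontrolled design. None of this removes the ambiguity in an HRV change taken alone.

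**Conclusion.** The point holds as a limit on interpretation. As planned, a change in mean HRV under hypothesis 2 cannot be separated from a change in movement. The comparison is before-after on a recording made at home, no control condition is described, and no analysis step uses concurrent activity.

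Neither sign nor size can be derived from the documents. The illustrative false-positive rate of 15% to 26% rests on an assumed 15 ms still/moving gap in RMSSD, a 10-point rise in still share and an SD of change of 6 ms. A smaller gap or heavy loss of moving epochs brings it to about 6% to 9%, close to the nominal 5%. If HRV and movement are uncoupled, or activity does not differ between the two days, there is no bias. This is an inexpensive improvement to the analysis plan and does not show the hypothesis to be invalid.

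**What to change.** In Section VI:

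1. Name the HRV metric for hypothesis 2, for example RMSSD in 5-minute epochs.
2. Keep the unadjusted post- versus pre-treatment comparison.
3. Report beside it either the same comparison restricted to low-movement epochs, or a subject-level mixed model with concurrent accelerometer activity as a time-varying covariate.
4. State that, because reduced movement is itself a hypothesised effect, the activity-matched result estimates the HRV change not explained by movement. Describe an HRV change as distinct from reduced movement only where that result is consistent with it.

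The cost is some extra programming, since HRV and actigraphy are already recorded together. The low-movement version uses less of the recording and so loses some precision. There is no added burden on participants.
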